### 4.4 Compliance with Laws and Regulations

The study will be conducted in accordance with U.S. Food and Drug Administration and International Conference on Harmonization Guidelines for Good Clinical Practice, the Declaration of Helsinki, any applicable local health authority, and IRB requirements. The PI or designee will be responsible for obtaining continuing and not less than annual IRB re-approval throughout the duration of the study. Copies of the investigator's annual report to the IRB and copies of the IRB continuance of approval must be maintained by the MCC CRO. The PI or designee is also responsible for notifying the Data and Safety Monitoring Committee (DSMC) of the MCC and the UK IRB of any significant adverse events that are serious and/or unexpected, as per standard operating procedure (SOP)'s of those entities. MCC DSMC will review all adverse events of this investigator-initiated trial (IIT) as per its SOP.

## **5. TREATMENT PLAN**

### **5.1 Enrollment and Screening Process**

Prior to any study-required tests, patients must first provide written informed consent to participate in this study.

All radiographic studies should be completed within 6 weeks prior to starting investigational agents.

Pre-study screening shall include:

- complete medical history and evaluation of ECOG Performance Status;
- EKG;
- pathological (biopsy) or cytologically proven SCLC;
- CT with contrast of chest and upper abdomen to include the liver and adrenals;

All lab tests should be completed within 2 weeks prior to study registration:

- CBC with differential;
- Serum chemistries to include: alkaline phosphatase, glucose, creatinine, electrolytes, TSH, AST (SGOT), ALT (SGPT), and total bilirubin (see Study Calendar for complete list).
- Serum or urine pregnancy test for women of childbearing potential.

## 5.2 Nivolumab and Rucaparib Administration

The recommended starting dose of rucaparib as a continuously administered oral monotherapy is 600 mg BID. Patients may take rucaparib with or without food. Each dose should be taken with approximately 8 oz. (240 mL) of room temperature water. Tablets should be swallowed whole without crushing or chewing. Patients should take rucaparib doses as close as possible to 12 hours apart, preferably at the same time every day. If a patient misses a dose (i.e., does not take it within 4 hours of the scheduled time), the patient should skip the missed dose and resume by taking the next scheduled rucaparib dose. Missed or vomited doses should not be made up.

Modification of rucaparib dose may be a necessary component of AE management, and study-specific protocol guidelines for dose modifications should be followed. See Section 6.

Nivolumab will be administered as intravenous infusion once every 4 weeks at fixed dose of 480 mg. The FDA has approved a supplemental biologics license application adding a 4-week dosing schedule for nivolumab (Opdivo) across several of the PD-1 inhibitor's indications (non-small cell lung cancer, renal cell carcinoma, metastatic urothelial carcinoma, Hodgkin lymphoma, metastatic squamous cell carcinoma and hepatocellular carcinoma). Adding a q 4 weekly regimen will be convenient for patients and will be more cost effective as it will reduce number of visits to infusion center. We have had no problem with using q4 week dosing in SCLC at our center. No dose modification will be allowed (other than hold or discontinue). Please refer to Section 6 for guidance regarding Nivolumab schedule in response to toxicity.

## 5.3 Drug-drug Interactions

### 5.3.1 Cytochrome P450 Isoenzyme Inhibitors, Inducers, and Substrates

Based on the results from the in vivo CYP interaction study (CO-338-044), rucaparib is a moderate inhibitor of CYP1A2, and a weak inhibitor of CYP2C9, CYP2C19, and CYP3A. Caution should be used with concomitant medications that are sensitive clinical substrates of CYP1A2, CYP2C9, CYP2C19, and/or CYP3A (see IB for rucaparib). Although in vitro rucaparib metabolism mediated by CYP3A4 was slow, a significant contribution of CYP3A4 in vivo cannot be excluded. Caution should be used for concomitant use of strong CYP3A4 inhibitors or inducers such as **voriconazole**, **clarithromycin** etc. (see the FDA website for a list of examples of sensitive clinical substrates and strong perpetrators of the above--mentioned enzymes). Selection of an alternative concomitant medication is recommended, and concomitant medication use among study participants will be monitored by study staff and the study PI.

### Effects of Rucaparib on Other Medicinal Products or Concomitant Drugs

At the steady-state following treatment with 600 mg rucaparib BID, rucaparib is a moderate inhibitor of CYP1A2, and a weak inhibitor of CYP2C9, CYP2C19, and CYP3A. Rucaparib also marginally inhibits P-gp in the gut, but this is unlikely to be clinically significant.

**CYP1A2 Substrates** When co-administering medicinal products metabolized by CYP1A2, particularly medicines that have a narrow therapeutic index (e.g., tizanidine, theophylline), dose adjustments may be considered based on appropriate clinical monitoring.

**CYP2C19 Substrates** No dose adjustment is considered necessary for co-administered medicinal products that are CYP2C19 substrates. **CYP3A Substrates** Caution is advised when co-administering

medicinal products that are CYP3A substrates with a narrow therapeutic index (e.g., alfentanil, astemizole, cisapride, cyclosporine, dihydroergotamine, ergotamine, fentanyl, pimozone, quinidine, sirolimus, tacrolimus, terfenadine). Dose adjustments may be considered, if clinically indicated based on observed AEs.

**P-gp Substrates** No dose adjustment is recommended for co-administered medicinal products that are P-gp substrates.

**Other Enzymes and Transporters** Interaction of rucaparib with other enzymes and transporters was evaluated in vitro. Rucaparib is a weak inhibitor of CYP2C8, CYP2D6, and UGT1A1. Rucaparib down regulated CYP2B6 in human hepatocytes at clinically relevant exposures.

In vitro, rucaparib is a potent inhibitor of MATE1 and MATE2-K, a moderate inhibitor of OCT1, and a weak inhibitor of OCT2. As inhibition of these transporters could increase metformin renal elimination and decrease liver uptake of metformin, caution is advised when metformin is co-administered with rucaparib.

In addition, rucaparib is an inhibitor of the BCRP with an IC50 value suggesting potential BCRP inhibition and increased exposures of medicinal products that are BCRP substrates (e.g., rosuvastatin).

**Effect of Food on Rucaparib Exposures:** A high-fat meal increased Cmax by 20% and increased AUC0-24 by 38%. The effect is not considered clinically significant. In clinical studies, rucaparib was administered with or without food.

There were no meaningful changes in cytokines known to have indirect effects on CYP enzymes across all dose levels of nivolumab (0.3, 2 and 10 mg/kg) during the course of treatment. This lack of cytokine modulation suggests that nivolumab has no or low potential for modulating CYP enzymes, thereby indicating a low risk of therapeutic protein-drug interaction.

### 5.3.2 Anticoagulants

Rucaparib is a weak inhibitor of CYP2C9 in vivo. Warfarin, Coumadin, Tizanidine and Aripiprazole are exclusion criteria for study eligibility. Use of similar medications inhibiting CYP2C9 will be reviewed by the treating investigator to determine eligibility and additional monitoring for AEs if patient is enrolled on-study.

### 5.3.3 Other Concomitant Medications

Therapies considered necessary for the patient's well-being may be given at the discretion of the investigator and should be documented on the eCRF. Other concomitant medications should be avoided, except for analgesics, chronic treatments for concomitant medical conditions, or agents required for life-threatening medical problems.

- **Herbal and complementary therapies** should be discouraged because of potential for unknown side effects and adverse drug interactions, but any that are taken by the patient should be documented appropriately on the eCRF.

- Rucaparib marginally increased **digoxin** area under the plasma concentration-time curve (AUC) by 20%. Caution should be exercised for patients receiving rucaparib and requiring concomitant medication with digoxin. Patients taking digoxin should have their digoxin levels monitored after starting rucaparib and then regularly per standard clinical practice.
- In vitro, rucaparib is a potent inhibitor of MATE1 and MATE2-K, a moderate inhibitor of OCT1, and a weak inhibitor of OCT2. As inhibition of these transporters could increase metformin renal elimination and decrease liver uptake of **metformin**, caution is advised when metformin is co-administered with rucaparib.
- In addition, rucaparib is an inhibitor of the BCRP with 50% inhibitory concentration (IC50) value suggesting potential BCRP inhibition and increased exposures of medicinal products that are BCRP substrate (e.g., **rosuvastatin**).

#### 5.4 Duration of Therapy

In the absence of treatment delays due to adverse event(s), treatment may continue for *24 months* or until one of the following criteria applies:

- Disease progression,
  - Intercurrent illness that prevents further administration of treatment,
  - Unacceptable adverse event(s),
  - Patient decides to withdraw from the study, or
  - General or specific changes in the patient's condition render the patient unacceptable for further treatment in the judgment of the investigator
- The date and the reason for removal from study treatment must be documented in the Case Report Form.

#### 5.5 Duration of Follow-Up

Patients will be followed until death or 3 years after registration for survival, whichever occurs first. Patients removed from study therapy due to unacceptable adverse event(s) will be followed per protocol, until resolution or stabilization of the adverse event.

#### 5.6 Criteria for Removal from Study

Patients will be removed from study therapy when any of the criteria listed in Section 5.4 applies and followed per section 5.5. The reason for study therapy removal and the date the patient was removed must be documented in the Case Report Form.

## 6. DOSING DELAYS/DOSE MODIFICATIONS

Doses of oral study drug (rucaparib), and/or IV study drug (nivolumab), may be interrupted or delayed for toxicity and other protocol-specified criteria. **Dose reductions are permitted for Rucaparib, but not for Nivolumab.** The assessment for delay or discontinuation should be made separately for the oral study drug (rucaparib) and the IV study drug (nivolumab) where class-specific safety profiles do not overlap; however, if toxicity is considered related to all study drugs or if the investigator is unable to determine which study drug is the cause of the AE, then all study drugs in the combination should be delayed and/or discontinued. For management of AEs which can be clearly attributed to rucaparib OR nivolumab, independent dose modification for either agent is allowed. If the relationship to an AE that is common to both drugs can be clearly distinguished, then a recommendation from the ET CCART for continuation of the non-offending drug can be requested by the investigator. Treatment may be prematurely discontinued due to withdrawal of consent, unacceptable toxicity, disease progression, completion of treatment cycles, or termination of the study, whichever occurs first.

Dose modification and re-treatment of oral and/or IV study drug are to be based on criteria presented in Table 4.

**Table 4. Dose Modification and Re-treatment Criteria for Oral and IV Study Drugs**

| Adverse Event  | Severity (CTCAE Grade) | Oral Study Drug (rucaparib)    |                        | IV Study Drug (nivolumab)      |                                    |
|--|------------------------|--------------------------------|------------------------|--------------------------------|------------------------------------|
|  |                        | Dose Modification  | Re-treatment           | Dose Modification  | Re-treatment                       |
| Non-hematological Non-skin AEs  |                        |                                |                        |                                |                                    |
| Adverse event, except fatigue  | 2                      | None                           | N/A                    | Hold                           | Grade ≤ 1 or baseline  |
| Any adverse event (related events lasting > 7 days for nivolumab, exceptions below)  | 3 or 4                 | Hold                           | ≤ Grade 2  | Discontinue                    |                                    |
| Exceptions with rucaparib   |                        |                                |                        |                                |                                    |
| Nausea, Vomiting, Diarrhea adequately controlled with systemic antiemetics/antidiarrheal medications lasting <7 days.  | 3               | None                           |                        |                                |                                    |
| ALT/AST provided no signs of liver dysfunction (see laboratory section below)  | 3                      | None                           |                        |                                |                                    |
| Exceptions with nivolumab   |                        |                                |                        |                                |                                    |
| Uveitis, pneumonitis, bronchospasm, neurological toxicity, hypersensitivity reaction or infusion reaction of any duration                                      | 3                      |                                |                        | Discontinue                    |                                    |
| Endocrinopathies, adequately controlled with only physiologic hormone replacement  | 3                      |                                |                        | Hold                           | Grade ≤ 1 or baseline  |
| Drug-related adrenal insufficiency or hypophysitis   | 2                      |                                |                        | Hold                           | Grade ≤ 1 or baseline  |
| Adrenal insufficiency regardless of control with hormone replacement   | 3                      |                                |                        | Discontinue                    |                                    |
| Laboratory abnormalities except as specified below   | 3                      |                                |                        | Hold                           | Grade ≤ 1 or baseline  |
| Drug-related ALT, AST, or bilirubin  | 3                      |                                |                        | Discontinue        |                                    |
| Adverse event or laboratory abnormality except for those below that do not require delay   | 4                      |                                |                        | Discontinue                    |                                    |
|  |                        |                                |                        |                                |                                    |
| Isolated electrolyte imbalances/abnormalities not associated with clinical sequelae/corrected w/supplementation /appropriate management w/in 72 hours of onset | 3               |                                |                        | Hold                           | Grade ≤ 1 or baseline  |

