Patients may resume treatment with IV study drug when the drug-related AE(s) improve to Grade ≤ 1 or resolve to baseline value, with the following exceptions which are allowed: Grade 2 fatigue, Grade 2 skin toxicity (if no Grade 3 drug related skin AE). For patients with Grade 2 AST, ALT, or total bilirubin elevations, dosing may resume when laboratory values return to baseline and management with corticosteroids, if needed, is complete. Drug-related pulmonary toxicity, diarrhea or colitis must have resolved to baseline before treatment is resumed. Patients with persistent Grade 1 pneumonitis after completion of a steroid taper over at least 1 month may be eligible for retreatment if discussed with and approved by the study medical monitor. Patients with drug-related endocrinopathies adequately controlled with only physiologic hormone replacement may resume treatment after consultation with the study medical monitor. Adrenal insufficiency requires discontinuation regardless of control with hormone replacement.

The patient may continue at same or reduced dose at the discretion of the investigator. If treatment is resumed at the same dose, and the patient experiences the same toxicity, treatment should be interrupted, then resumed at a reduced dose following improvement of the event to ≤ CTCAE Grade 2. If the patient continues to experience toxicity, additional dose reduction steps are permitted; however, the investigator should consult with the sponsor's medical monitor before reducing to 300 mg BID.

In most cases of Grade 3 ALT or AST elevation, IV study drug will be permanently discontinued. For patients with Grade 3 ALT or AST elevations after the start of IV dosing, but on a background of previous elevations on the first cycle of oral study drug, IV study drug hold is required, but discontinuation is not required, if ALT/AST elevations begin to resolve before the next scheduled infusion, and toxicity is considered to be mainly related to oral study treatment, after the investigator discusses the case with the study medical monitor. Levels will be monitored every 3 days; if they continue to rise more than 20%, the Hepatic Adverse Event Management Algorithm for a Grade 3 event will be followed. Treatment with IV drug may be resumed if levels return to Grade 2. If total bilirubin elevations > 2 × ULN accompany any of the ALT/AST elevations, IV drug should be discontinued.

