#### 7.1.1 Supportive care guideline for rucaparib and nivolumab toxicity

**Opportunistic Infections:** It is rare for a patient receiving immunosuppression for nivolumab-related AEs to develop an opportunistic infection. Subjects with inflammatory events of any organ category expected to require more than 4 weeks of corticosteroid or other immunosuppressive agents to manage the AE should be considered for antimicrobial/antifungal prophylaxis, per institutional guidelines, to prevent opportunistic infections such as *P. jiroveci* (formerly *P. carinii*) and fungal infections.

**Immune-Mediated Pneumonitis:** Nivolumab can cause immune-mediated pneumonitis, defined as requiring use of corticosteroids and no clear alternate etiology. Fatal cases have been reported. Monitor patients for signs with radiographic imaging and for symptoms of pneumonitis. Administer corticosteroids at a dose of 1 to 2 mg/kg/day prednisone equivalents for moderate (Grade 2) or more severe (Grade 3-4) pneumonitis, followed by corticosteroid taper. Please refer to section 6 for dose modification guidance.

**Immune-Mediated Colitis:** Nivolumab can cause immune-mediated colitis, defined as requiring use of corticosteroids with no clear alternate etiology. Monitor patients for signs and symptoms of colitis. Administer corticosteroids at a dose of 1 to 2 mg/kg/day prednisone equivalents followed by corticosteroid

taper for severe (Grade 3) or life-threatening (Grade 4) colitis. Administer corticosteroids at a dose of 0.5 to 1 mg/kg/day prednisone equivalents followed by corticosteroid taper for moderate (Grade 2) colitis of more than 5 days duration; if worsening or no improvement occurs despite initiation of corticosteroids, increase dose to 1 to 2 mg/kg/day prednisone equivalents. Refer to section 6 for dose modification guidance.

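### Table 4 mandates a nivolumab hold at Grade 2, but leaves a short, unlisted Grade 3 event clearly attributed to nivolumab with only a discretionary hold

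*Combined protocol and SAP*

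**What the plan says.** Section 6 states: "Dose modification and re-treatment of oral and/or IV study drug are to be based on criteria presented in Table 4". In Table 4, the block for non-hematological, non-skin events reads as follows.

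- **Grade 2**, "Adverse event, except fatigue": nivolumab Hold, with re-treatment at Grade 1 or below or at baseline. The row states no duration or relatedness condition, and its severity cell is 2 only.
- **Grade 3 or 4, general row**, "Any adverse event (related events lasting > 7 days for nivolumab, exceptions below": nivolumab Discontinue.
- **Grade 3, exception for rucaparib**, "Nausea, Vomiting, Diarrhea adequately controlled with systemic antiemetics/antidiarrheal medications lasting <7 days": rucaparib None; the nivolumab cells are empty.
- **Grade 3, exceptions for nivolumab**, none tied to the 7-day condition: "Uveitis, pneumonitis, bronchospasm, neurological toxicity, hypersensitivity reaction or infusion reaction of any duration" (Discontinue); "Endocrinopathies, adequately controlled with only physiologic hormone replacement" (Hold); adrenal insufficiency (Discontinue); drug-related ALT, AST or bilirubin (Discontinue, subject to footnote 5); other laboratory abnormalities and isolated electrolyte abnormalities (Hold).
- **Grade 4**: a separate nivolumab row says Discontinue, with no duration test.

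Footnote 2 adds that nivolumab should be held whenever the investigator judges that an event warrants it. Footnote 3 governs resumption and includes: "Drug-related pulmonary toxicity, diarrhea or colitis must have resolved to baseline before treatment is resumed". Section 7.1.1 calls for corticosteroids followed by a "taper for severe (Grade 3) or life-threatening (Grade 4) colitis", and refers to Section 6 for dose modification. The opening text of Section 6 says that all study drugs are to be delayed and/or discontinued when toxicity is related to all of them or its cause cannot be determined.

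**The concern.** A dose-modification table should not become less binding as the same toxicity gets worse. Here a Grade 2 colitis triggers a required nivolumab hold. A Grade 3 colitis in its first week triggers nothing that the table requires, because the only general row for that grade waits until the event has passed 7 days. The condition also cannot be judged on the day it matters if an infusion falls due inside that week.

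Read literally, the table would allow an infusion during an active Grade 3 immune event that would have required a hold one grade lower. In practice investigators would fill the gap individually, so handling would vary between patients in a trial that has the toxicity profile of the combination as a secondary objective (1.2.4).

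**Working it through.** The plan states no figure on this point. The check is a coverage reading of the nivolumab column, followed by a rough size.

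**Coverage, non-hematological non-skin block**

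| Event | Required nivolumab action |
|---|---|
| Grade 2, any duration, except fatigue | Hold |
| Grade 3, in a named exception, any duration | Hold or Discontinue, by row |
| Grade 3, related, unlisted, over 7 days | Discontinue |
| Grade 3, related, unlisted, 7 days or less, or duration not yet known | No row |
| Grade 4, any duration | Discontinue |

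Three places could fill the empty line.

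1. *Footnote 2.* It applies to the whole nivolumab column, but it turns on the investigator's judgement and is written as an addition to the table's criteria. It supplies a discretionary hold.
2. *The Section 6 all-drugs rule.* It covers shared or undeterminable cause. A colitis clearly attributed to nivolumab falls outside it.
3. *Footnote 3 and Section 7.1.1.* Footnote 3 sets a condition for resuming after diarrhoea or colitis, so it presupposes an interruption. Among the rows that reach these events, only the Grade 2 row imposes one from which treatment can resume. Section 7.1.1 supplies no dosing action for colitis and points back to Section 6.

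**A second conflict.** Section 7.1 lists diarrhoea as expected for both drugs. For Grade 3 diarrhoea of shared or undeterminable cause, controlled and under 7 days, the Section 6 text says delay and/or discontinue all drugs, while Table 4 gives None for rucaparib.

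**Size.** Inputs: 36 patients (Section 11.1); nivolumab every 4 weeks, or 28 days (Section 5.2). Assumptions: 10–20% of patients have one such event, and onset is uniform over the cycle.

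- Patients with such an event: 36 × 0.10 = 3.6 to 36 × 0.20 = 7.2.
- Share of onsets in the 7 days before an infusion: 7/28 = 25%. This is a ceiling, because the event must still be at Grade 3 on infusion day.
- Patients facing an infusion with the question open: 3.6 × 0.25 = 0.9 to 7.2 × 0.25 = 1.8.
- If durations are instead uniform over 0–7 days (mean 3.5 days), the share is 3.5/28 = 12.5%, giving 3.6 × 0.125 = 0.45 to 7.2 × 0.125 = 0.9.

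**The case against.** The strongest defence is that the table is far from silent on Grade 3. Many Grade 3 events have an action at any duration, skin events have their own Hold row, Grade 4 is covered, footnote 2 lets the investigator hold for anything, and the all-drugs rule will often apply to diarrhoea. All of this stands and limits the point. It does not give a required action for a short, unlisted Grade 3 event clearly attributed to nivolumab.

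A reader might infer more than the documents support:

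- *That the rule weakens with severity in general.* It does not. The break is confined to one class of Grade 3 events, and the change is from a mandatory hold to a discretionary one.
- *That the empty nivolumab cell in the nausea, vomiting and diarrhoea row means no action, so that neither drug is held.* Blank cells in the exception rows are a layout feature. The neighbouring Grade 3 ALT/AST row is blank for nivolumab too, yet other rows give Discontinue, and where no nivolumab action is meant the table says None (Grade 3 lymphopenia, or asymptomatic amylase or lipase).
- *That Section 6 has no entry for colitis.* It covers Grade 2, related Grade 3 beyond 7 days, and Grade 4.
- *That unrelated Grade 2 events require a hold while unrelated Grade 3 events do not.* The Grade 2 row states no relatedness limit, but footnote 3 speaks of drug-related events when lifting a hold. This is an ambiguity, not an established inversion.
- *That 4–7 patients are affected.* That is the assumed number having such an event at all, before asking whether an infusion falls due during it.

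**Conclusion.** The point holds in narrow form. For a Grade 3 non-hematological, non-skin, non-laboratory event clearly attributed to nivolumab, outside the named exceptions and not known to exceed 7 days, Table 4 requires less than it does at Grade 2. That does not fit footnote 3 or Section 7.1.1. The rucaparib conflict for Grade 3 diarrhoea of shared or undeterminable cause is separate and also needs resolving.

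The expected number is about 1–2 of 36 patients at most. It rests on an assumed 10–20% event rate that the documents do not give and on uniform onset. The textual gap does not depend on that count. Sample size, PFS and the stated precision are unaffected, and Section 11.2 plans no analysis of holds or exposure. This is a safety-wording defect, worth correcting because the table is binding.

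**What to change.** The sponsor's clinical team should reconcile the Grade 2 row, the general Grade 3 or 4 row, the Grade 3 nausea, vomiting and diarrhoea exception, footnotes 2 and 3, the Section 6 attribution rule and Section 7.1.1. The revised text should:

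- give a nivolumab entry for every grade and duration;
- say what applies while it is not yet known whether an event will exceed 7 days;
- say whether the Grade 2 row is limited to related events;
- say whether the Section 6 text or the Table 4 entry governs rucaparib for controlled Grade 3 diarrhoea of shared or undeterminable cause.

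Which action applies is a clinical decision, and none is proposed here. The cost is table and footnote wording in one amendment, with no added patients, visits or data.
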